4.4 Applicable Endpoint Definitions

Access Abandonment (permanent abandonment) is defined as the point at which the access can no longer be used for one or two needle prescribed HD as it may be unable to provide adequate flows and / or is deemed unsafe for the participant, and the associated problem cannot be corrected by any further intervention, including medical, surgical, or endovascular interventions or rest.^{8,19} Participants with an abandoned index AVF will continue with follow-up through 24-months and data will be collected on safety and interventions.

A HD AV access is not considered abandoned:

- If the participant discontinues use of the AV access due to kidney transplant, initiation of PD, or participant preference.
- During the maturation period or while waiting for a second stage procedure unless the principal investigator (PI) determines the participant requires and they then receive an alternative HD vascular access.

- During planned interventions, including transposition.
- If all reasonable efforts have not been attempted (and documented) to improve the condition of the access for it to be used.

A discontinuation of use of the clinical investigation AVF for any reason that does not meet this definition of access abandonment will be considered a temporary interruption.

Access Circuit Censoring Events include participant transfer to PD, kidney transplantation or the event of a participants premature discontinuation in the investigation due to withdrawn consent, withdrawal by PI, Lost to Follow-Up (LTF), or participant death (refer to Section 6.5 for definitions).

Adjunctive Procedure(s): Procedure(s) completed during the index procedure (prior to leaving the procedure room) as part of Standard-of-Care (SOC) procedures. These may include procedures to facilitate maturation and / or cannulation of the AVF, procedures to maintain use of the AVF, procedures to ensure HD continuity, as well as procedures to address AFs.

Second Stage Procedure(s): Facilitation Interventions (as defined below) intended to support the cannulation of arterialized vein segments that are determined to be needed a priori to or at the time of the index procedure (i.e. pre-planned facilitation interventions intended to support cannulation). Second stage procedures will not count against the intervention or patency endpoints and will require completion of the Second Stage Procedures eCRF.

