## 2.4 Sample Size

The sample size for the investigation of one-hundred and fifty (150) treated participants was established to assure adequate power for the primary safety and effectiveness endpoints as well as to result in a sufficient sample size (when accounting for attrition) for assessment of the secondary and exploratory endpoints, specifically for those that only apply to subsets of the overall population (i.e., the incident population and wrist arterial procedure access population).

- 1) Primary Safety Endpoint The proportion of participants with freedom from device- or procedure-related SAEs through 30 days (ITT Population).
  - Assumptions:
    - The freedom from device- or procedure-related SAE rate for AVFs created using the WavelinQTM EndoAVF System is estimated at 92.6% through 30 days based on pre-market data;
    - The PG is set at 82.6% using a 10% non-inferiority margin;
    - o The rate of attrition through 30 days is assumed to be 10%; and
    - o The Type 1 error is 0.05 (two-sided).
  - Sample Size:
    - o A sample size of 150 treated participants [135 evaluable] will give over 92.5% power with a two-sided type I error of 0.05 as calculated using PASS 2019 (One Proportion Exact Test).
- 2) Primary Effectiveness Endpoint Interventions Post Creation to Facilitate AVF Use and / or Maintain AVF Use (Facilitation and / or Maintenance Interventions) through the Timepoint of the 6-Month Follow-Up of the Last Active Treated Participant (AT Population)
  - Assumptions:
    - The number of interventions post creation to facilitate AVF use and / or maintain AVF use after AVF creation using the WavelinQTM EndoAVF System is estimated at 3.0 / PY, a conservative assumption based on pre-market data;
    - The PG is set at 5 / PY to align with the targets and recommendations of the 2019 update of the KDOQI Clinical Practice Guideline for Vascular Access of ≤ 2 interventions to facilitate and ≤ 3 interventions to maintain AVF use:
    - The rate of attrition through 6-, 12-, and 24-months, including lost to follow-up, death, and other clinical investigation premature withdrawals is assumed to be 20%, 40%, and 60%, respectively; and
    - o The Type 1 error is 0.05 (two-sided).
  - Sample Size:

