    - O A sample size of 150 treated participants, yielding more than 100 PY by the time the last active treated participant completes their 6-month follow-up, will give over 99% power with a two-sided type I error of 0.05 as calculated using PASS 2019 (One-Sample Poisson Rate Test).

Hence, the sample size of 150 treated participants will provide approximately 92.5%\*99%= 91.5% power for the co-primary endpoints.

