## 2.7 Endpoints

Note: The term access abandonment is synonymous with permanent abandonment for the purposes of these investigation documents. Access abandonment (permanent abandonment) is an abandonment that meets the definition in Section 4.4 of the CIP. The term access discontinuation is used to refer to any discontinuation of use of the access that does not meet these criteria of the definition and may also be referred to as a "temporary interruption" as per the CIP.

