Length of investigation duration (Days) is from the date of index procedure to the cutoff date of database lock (cutoff date – date of index procedure +1). If a participant discontinued early, then the last date of available study data (including the unscheduled visit date) will be used to calculate the length of investigation duration (last date of

available study data – date of index procedure +1). If a participant's endoAVF has permanent abandonment the date of permanent abandonment will be used to calculate the length of investigation duration (permanent abandonment date – date of index procedure +1).

The primary effectiveness analysis will be conducted on the AT population after the last active treated participant completes their 6-month follow-up; by this time, all participants still in the clinical investigation will have at least 6-months of data. The number of Facilitation and / or Maintenance Interventions per PY will be estimated by Poisson regression model with only the intercept term, and the estimate and 95% CI will be provided using the Wald method, and the p-value comparing to the PG will be calculated by a Chi-square test. The analysis will be repeated on the PP population.

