#### **5.2.4** Cumulative Functional Patency

The time interval of cumulative functional patency is defined as the time from first successful HD AV access use for HD using 2-needle cannulation to access abandonment. This endpoint will be evaluated through 12-months. Additionally, for exploratory purposes, the endpoint will be evaluated through 6 months, 18 months, and 24 months.

Only the participants who have started 2-needle HD using the endoAVF will be considered as evaluable for this endpoint.

Access Abandonment (Permanent Abandonment) will be identified if:

On the EndoAVF Dialysis page, Date endoAVF Successfully Used with 2 Needles for Hemodialysis is not NULL and within a specific visit (e.g., within 395 days for 12 months).

and

On the EndoAVF Abandonment page, Date of Abandonment is not NULL and within a specific visit (e.g. within 395 days for 12 months), the question of "All Possible Attempts Have Been Made to Improve the Condition of the Access" is checked as Yes, and the question of "Could Further Endovascular Interventions

Salvage the Access" is checked as No, and the question of "Could Further Surgical Revisions Salvage the Access?" is checked as No, and Reason for Abandonment is selected as "The Access is No Longer Viable" or "The Access is Viable but there are Complications that Require the Abandonment of the Access".

The binary definition for cumulative functional patency is shown as below:

- If permanent abandonment, as detailed above, occurs on, or before, a specific visit (e.g., 365+30 = Day 395 for 12 months post creation), the participant is considered as having an event (loss of cumulative functional patency).
- If the participant was transferred to PD, or had a kidney transplant, or had access discontinuation, or discontinued before the beginning of a specific visit (e.g., 365-30 = Day 335 for 12 months post creation) without permanent abandonment, the participant is considered not evaluable and will not be included in the analysis.
- Otherwise, if the participant did not have permanent abandonment and has passed the specific visit window by the cutoff date of database lock, the participant is considered as not having an event.

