## 5.3.14 HD AV Access Continuity

HD AV access continuity is defined as the ability for a participant to receive an alternate HD AV access in the same arm as the index AVF. This endpoint applies to AT population participants for whom their index AVF is abandoned. The alternate type(s) of HD AV access(es) placed in these participants will be collected.

The participants for whom their index AVF is abandoned or in whom they have access discontinuation will be identified if:

On the EndoAVF Abandonment eCRF page, Reason for Abandonment is not NULL.

Ana

On the Post-Procedure Intervention eCRF page, the question of "Was a New Vascular Access Created" is checked as Yes.

The counts and percentages of the alternate type(s) of HD AV access(es) will be summarized.

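### A fistula that is replaced or given up without formal permanent abandonment keeps adding person-time to the co-primary intervention rate, which pulls the rate towards meeting 5/PY

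*SAP*

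**What the plan says.** The co-primary effectiveness endpoint is the rate of facilitation and maintenance interventions per PY. It is estimated by an intercept-only Poisson model and tested against a performance goal (SAP 5.1.2). SAP 2.4 states: "The PG is set at 5 / PY to align with the targets and recommendations". The planning rate "is estimated at 3.0 / PY, a conservative assumption based on pre-market data".

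Person-time runs from the index procedure to the database-lock cutoff, with two exceptions. Early discontinuation from the study ends it at the last available data. The other exception concerns the fistula itself: "If a participant's endoAVF has permanent abandonment the date of permanent abandonment will be used to calculate the length of investigation duration".

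SAP 2.7 takes permanent abandonment from protocol 4.4. It uses access discontinuation, or temporary interruption, for "any discontinuation of use of the access that does not meet these criteria". Under protocol 4.4 an access is not abandoned if use stops by participant preference, or "If all reasonable efforts have not been attempted (and documented) to improve the condition of the access for it to be used". It is also not abandoned during maturation or while a second stage procedure is awaited, unless the investigator determines that an alternative access is required and the participant then receives one.

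SAP 5.2.4 and 5.3.7 turn the definition into eCRF criteria. The item "All Possible Attempts Have Been Made to Improve the Condition of the Access" must be Yes, both salvage questions (endovascular and surgical) must be No, and one of two listed reasons must be selected. SAP 5.2.4 additionally requires a recorded date of 2-needle use.

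Under protocol 4.4 and Table 1, placing a replacement AVF or AVG is an HD continuity intervention and is not counted in the primary endpoint. Later procedures on the replacement are not counted in any category.

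**The concern.** Suppose a participant stays in follow-up, the index fistula falls out of use, and a new AVF or AVG is placed, but one abandonment criterion is not met. Under SAP 5.1.2 the clock runs on. Work on the new access cannot enter the numerator, and there is usually little reason to keep working on the old one. The added time carries few or no countable events, so the rate falls.

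The direction favours success, and in a single-arm trial against a fixed goal no comparator cancels it. There is also an awkward incentive. Fewer salvage attempts mean fewer counted interventions, a lower chance that the loss qualifies as abandonment, and more event-free time.

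The SAP already anticipates these participants. Section 5.3.14 covers those with abandonment or access discontinuation for whom "Was a New Vascular Access Created" is Yes.

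**Working it through.** **1. How the SAP treats the same event elsewhere**

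- *Censors or excludes at access discontinuation:* the supportive Kaplan-Meier safety analysis (5.1.1), physiological maturation (5.2.2), cannulation success (5.2.3), cumulative functional patency (5.2.4), primary patency (5.3.7) and cumulative patency (5.3.8).
- *Keeps time after abandonment, with a reason:* All Interventions Post Creation (5.3.6, item 3), because HD continuity interventions can still occur then. The SAP contrasts this with facilitation and maintenance interventions.
- *Does not stop at access discontinuation or replacement:* the co-primary rate (5.1.2).

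The principle that time should match the events that can be counted is therefore already in the SAP. It is applied in 5.1.2 to permanent abandonment only.

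**2. The plan's own figures**

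Inputs (SAP 2.4; protocol section 3 for enrolment): 150 participants, 18 months of enrolment, attrition of 20/40/60% at 6/12/24 months, goal 5/PY, planned rate 3.0/PY, two-sided alpha 0.05. Enrolment is taken as uniform, so potential follow-up at the cutoff is uniform on 6 to 24 months.

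*Attrition linear between the stated points.* Mean follow-up is 7.6 months for those with 6 to 12 months of potential follow-up and 12.8 months for those with 12 to 24.
(6 × 7.6 + 12 × 12.8)/18 = 11.07 months; 150 × 11.07/12 = 138 PY.

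*All of each interval's attrition at its start.* The two means are 6.6 and 10.8 months.
(6 × 6.6 + 12 × 10.8)/18 = 9.4 months; 150 × 9.4/12 = 117.5 PY.

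The plan's figure of more than 100 PY reproduces.

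*Success rule at 100 PY.* The upper Wald limit on the log scale must be below 5. With 456 events it is 4.56 × exp(1.96/√456) = 4.998, which passes; 457 events fail. The exact and score rules give the same cut. The chance of passing at a true 5/PY is P(Poisson(500) ≤ 456) = 2.5%. At 3.0/PY it exceeds 99.9%, so the stated power of over 99% also reproduces.

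**3. Effect of time out of service**

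Let f be the share of counted PY that falls after the index fistula is out of service and carries no countable events. Then

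observed rate = in-service rate × (1 − f).

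At 100 counted PY and a true in-service rate of 5/PY, the chance of passing is P(Poisson(500(1 − f)) ≤ 456):

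| f | Observed rate (/PY) | Chance of passing | Highest in-service rate that still passes, 4.56/(1 − f) |
|---|---|---|---|
| 0 | 5.00 | 2.5% | 4.56 |
| 2% | 4.90 | 6.4% | 4.65 |
| 5% | 4.75 | 19.9% | 4.80 |
| 10% | 4.50 | 62.3% | 5.07 |
| 15% | 4.25 | 93.5% | 5.36 |
| 20% | 4.00 | 99.7% | 5.70 |

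If the affected time carries countable events at some rate r, f is replaced by f(1 − r/5). With r = 2.5/PY, for example, 10% of such time acts like 5%.

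**4. Which abandonment rule applies in 5.1.2**

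Section 5.1.2 does not repeat the eCRF criteria. If the 5.2.4 version applied, a fistula lost before any 2-needle use could never stop the clock, because that version needs a 2-needle date. The 5.3.7 version does not. Protocol 4.4 allows abandonment when an alternative access is received during maturation, but neither set of SAP criteria has a route for that case if a salvage question is answered Yes.

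**The case against.** **The size is not known.** A reader might take the pre-market six-month cumulative patency of 77.3% (protocol 2.1.2), treat 22.7% as lost fistulas, and assume that some fraction miss the definition. The documents do not support this. They define cumulative patency as ending at abandonment, so if the pre-market figure used the same definition, the 22.7% are losses that already stop the clock. The losses at issue here would have been censored. This objection stands: no size can be derived from the plan.

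**The criteria may not govern 5.1.2.** A reader might infer that every eCRF criterion must be met before the primary clock stops. They are stated in 5.2.4 and 5.3.7, while SAP 2.7 points to protocol 4.4. The derivation for 5.1.2 may be in Appendix 2 (Derived Data Specification), which is not in the text available. Protocol 4.4 also allows some replaced fistulas to count as abandoned. This narrows the gap. It does not close it, because preference and incomplete efforts remain outside abandonment under protocol 4.4 itself.

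**Some of the time is genuinely at risk.** While salvage is possible, procedures to re-establish function count as maintenance interventions. A true interruption belongs in the denominator. This stands, and it is why replacement is a cleaner stopping point than loss of use.

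**The denominator is partly a choice.** Protocol 7.7.3 runs time to premature discontinuation with no stop at abandonment, and protocol 4.5.1 presents the endpoint as burden per PY. The SAP is already stricter than the protocol. This supports leaving the primary denominator alone and adding a sensitivity analysis.

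**Conclusion.** The point holds for mechanism and direction. Among participants still in the study, a fistula replaced or given up without meeting the permanent-abandonment definition adds time with few or no countable interventions, and this biases the rate towards meeting 5/PY. The size is unknown. The illustration (2.5% rising to about 20% at f = 5% and about 62% at f = 10%) assumes 100 PY, Poisson variation, a true in-service rate of exactly 5/PY and no countable events in the affected time.

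The test result is sensitive only if the in-service rate is near or above about 4.6/PY. At the planned 3.0/PY the test passes with or without the change, and only the reported estimate is affected. A reader might infer that the co-primary conclusion is unsafe as planned. The documents do not support that, since they give neither the share of time affected nor a reason to expect a rate close to the goal. This is an inexpensive improvement to the SAP.

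**What to change.** 1. In SAP 5.1.2, pre-specify a sensitivity analysis against 5/PY. End both person-time and event counting at the earliest of permanent abandonment, placement of a replacement AVF or AVG, or study exit, and otherwise at the data cutoff. Identify replacement from "Was a New Vascular Access Created" = Yes on the Post-Procedure Intervention page, restricted to AVF or AVG. Report the PY removed.
2. State in 5.1.2 which abandonment criteria apply, and that the 2-needle date required in 5.2.4 does not.
3. Reconcile the protocol 4.4 provision on an alternative access received during maturation with the eCRF criteria in SAP 5.2.4 and 5.3.7.

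Do not instead end time at access discontinuation when use never resumes and no later intervention is recorded. That rule selects time on the outcome: it deletes event-free time and keeps time with events. In a simulation of never-resumed participants (follow-up uniform on 0.5 to 2 years, discontinuation at a random point), true post-interruption rates of 1, 2 and 3/PY read about 1.8, 2.6 and 3.4.

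Cost: some SAP wording and one more denominator from fields already collected. The rate may be slightly less favourable and total PY falls. From 117.5 PY under early attrition, removing more than 17.5 PY (15%), including time already ended at abandonment, would take the total below 100.
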